5.5 Supportive care

- 1. G-CSF and erythropoetin administration: routine prophylactic use is not permitted. However, therapeutic use in patients with complications (severe neutropenia with fever or anemia), may be considered.
- 2. Steroids: should be used in the smallest dose to control symptoms of cerebral edema, and discontinued if possible.
- 3. Antiepileptic medications: should be used as indicated. Treatment with valproic acid is not allowed. Patients should preferably be treated with non-enzyme inducing antiepileptic medications to avoid any potential interactions with vorinostat. For patients on treatment with enzyme-inducing antiepileptic drugs, clinically relevant monitoring of drug levels is recommended, as considered appropriate by the treating physician.
- 4. Antiemetics: prophylactic and therapeutic use is allowed.
- 5. Other concomitant medications: therapies considered necessary for the wellbeing of the patient may be given at the discretion of the treating physician including prophylaxis for *pneumocystis carinii* pneumonia (PCP). All concomitant medications should be recorded.

6.0 PRE-STUDY EVALUATION

- **6.1** A complete history and neurological examination (including height, weight and Karnofsky Performance Status), as well as documentation of evaluable disease shall be performed on all patients within 14 days (+ 3 working days) of study entry.
- **6.2** The treating physician will review a Gd-DPTA MRI scan done prior to study entry documenting progression. For non-surgical arm patients, a baseline scan should be performed within 14 days (+ 3 working days) of registration, with day 0=registration date. The baseline on-study MRI should be performed on a steroid dosage that has been stable or decreasing for at least 5 days. If the steroid dose

is increased between the date of imaging and the initiation of therapy (or at that time), a new baseline MRI is required.

- **6.3** Pre-treatment laboratory tests will include CBC, differential, platelets, PT, PTT, INR, total protein, albumin, calcium, phosphorus, magnesium, glucose, BUN, creatinine, sodium, potassium, uric acid, total bilirubin, alkaline phosphatase, LDH, SGPT (ALT), SGOT (AST), amylase, lipase, lipid panel (total cholesterol, HDL-cholesterol, LDL-cholesterol, triglycerides), and a pregnancy test for women of child bearing potential (see 6.4 and Appendices I and J). Anticonvulsant levels in patients on treatment with enzyme-inducing antiepileptic drugs (phenytoin, phenobarbital, carbamazepine) will also be obtained if considered appropriate by the treating physician. Blood tests must be performed within 14 days (+ 3 working days) of registration, with day 0 = registration date. Pregnancy test must be obtained 24 hours before treatment with isotretinoin starts. Patients whose clinical condition has significantly changed between the time of these tests and the initiation of treatment in the judgement of the treating physician, will have a repeat chemistry panel prior to the start of treatment.
- **6.4** Patients will be enrolled in the mandatory iPLEDGE Program to initiate Isotretinoin (cRA) therapy. This program dictates guidelines for pregnancy testing and contraception in women of childbearing potential who are treated with cRA (please refer to Appendix I for iPLEDGE definition of woman of childbearing potential). However, it is anticipated that for the vast majority of patients with recurrent malignant glioma, strict adherence to these guidelines would imply unacceptable delays in their treatment. For this reason, in women of childbearing potential who elect to participate in this protocol, an "Exception Authorization for Oncology Patient" will be requested (Appendix J). This exception authorization will allow the patient to start treatment immediately after enrollment in iPLEDGE and obtention of a negative pregnancy test. The "Exception Authorization for Oncology Patient" will allow patients to expedite the beginning of therapy by eliminating the need for a 1 month delay in the first prescription of cRA.
- **6.5** Patients will complete the baseline MD Anderson Symptom Inventory-Brain Tumor Module (MDASI-BT) within 14 days (+ 3 working days) of study entry (*).
- **6.6** Patients enrolled on the phase II component of the trial will have blood samples collected for determination of acetylation status of histones and p21 levels in peripheral mononuclear cells before starting treatment (*).
- 6.7 If available, unstained paraffin tissue from surgical samples will be obtained. A representative paraffin tissue block (at least 5 mm x 5 mm) or 20 unstained paraffin slides will be obtained from original surgery, or definitive surgery, or the surgery closest to initiation of this clinical trial. Paraffin slides will be used to evaluate histone acetylation levels and p21 levels by immunohistochemistry. These will be correlated with response. If available, frozen tissue (≥ 1 g) from prior surgeries may also be sent for the same tests in frozen tissue (*).

* Note: **6.5**, **6.6** and **6.7** are optional procedures, and will be obtained if the patients gives his or her informed consent.

7.0 ON-STUDY EVALUATION

- 7.1 CBC, differential and platelets will be performed weekly (± 3 days) for the first cycle. If no significant toxicity is seen, monitoring will be changed to every two weeks (± 3 days) during treatment and prior to each new cycle. In addition, all patients will have the following tests every 2 weeks (± 3 days) for the first cycle and then every cycle as well as prior to each new cycle if no significant toxicities are noted: PT, PTT, INR, total protein, albumin, calcium, phosphorus, magnesium, glucose, BUN, creatinine, sodium, potassium, uric acid, total bilirubin, alkaline phosphatase, LDH, SGPT, SGOT. All patients will have serum amylase, lipase, and lipid panel drawn every 2 cycles of treatment. Patients may also be evaluated with labs at any time clinically indicated.
- **7.2** Patients on treatment with enzyme-inducing antiepileptic drugs (phenytoin, phenobarbital, carbamazepine) will be evaluated with anticonvulsant levels as considered appropriate by the treating physician.
- **7.3** A Gd-DPTA MRI scan shall be done after each **2 cycles** of treatment prior to initiating the next cycle. MRI scans may also be done at any time clinically indicated.
- 7.4 Physical and neurologic examinations will be performed after cycle 1 and cycle2, and subsequently after each 2 cycles of treatment prior to initiating the next cycle. Patients will also be evaluated anytime their clinical situation demands an assessment.
- **7.5** All patients receiving cRA must be enrolled in the iPLEDGE program (see Appendix I). Before starting treatment, an "Exception Authorization for Oncology Patient" will be requested for women of childbearing potential (Appendix J). A negative serum pregnancy test will be obtained 24 hours before initiation of treatment with cRA. Once treatment has started, pregnancy testing and counseling should occur monthly. If pregnancy does occur during cRA treatment, the drug must be discontinued immediately and the treating physician notified. The treating physician will in turn notify the study chair immediately.
- 7.6 The MDASI-BT will be completed at the time of physical and neurologic exam, i.e. after cycle 1 and cycle 2, and subsequently after every 2 cycles of treatment prior to initiating the next cycle of treatment. (*)
- **7.7** All relevant information regarding drug doses, concomitant medications and doses, measurable lesions, tumor response, laboratory examinations, and

treatment-related toxicities shall be documented in the patient's medical record and flow sheets.

- **7.8** After treatment on protocol is completed, patients will be followed for overall survival every 3 months, when possible.
- **7.9** All patients enrolled in the surgical arm of the phase II component of the trial will have tumor tissue and intraoperative blood samples (8ml) collected during surgery. Vorinostat will be given at 400 mg once daily for 3 consecutive days prior to surgery, with the last dose given on the morning of surgery within 6 hours of the tumor removal. Blood samples for acetylation status of histones and p21 levels in peripheral mononuclear cells will be collected on day 1 before (pretreatment), and at 1, 2 and 6 hours after administration of vorinostat.
- **7.10** Blood samples for acetylation status of histones and p21 levels in peripheral mononuclear cells should be collected before (pretreatment) and then 1, 2 and 6 hours after administration of vorinostat on day 1 of cycle 1, and before and within 4 hours after administration of vorinostat on day 1 of cycle 2 in patients enrolled in arms 1 and 3 of the phase II component (surgical and non-surgical patients). Total volume is 144 mL (6 x 24 mL)*.

*Note: 7.6 and 7.10 are optional procedures, and will be obtained if the patients gives his or her informed consent.

8.0 **RESPONSE CRITERIA**

The primary endpoint is Progression Free Survival (PFS) for determining the "winner" of the three regimens tested. Secondary endpoints are a) radiological response to treatment, b) the progression free survival at 6 months compared with historical controls, and c) overall survival. MRI brain scans will be used to define overall response or progression.

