3.1.7 Side Effects and Toxicities

Common side effects include arthralgias, back pain, cheilitis, conjunctivits, dry/itchy skin, dry mouth and epistaxis. Serious side effects include birth defects, depression, psychosis and, rarely, suicidal ideation, suicide attempts, suicide, and aggressive and/or violent behavior; pseudotumor cerebri, anaphylactic reactions, elevated triglycerides, pancreatitis, hearing impairment, hepatotoxicity, inflammatory bowel disease, neutropenia, rhabdomyolysis, decrease in bone mineral density and visual disturbances.

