5.1.1. Arm 1 – Vorinostat plus isotretinoin

This arm assessed the MTD of vorinostat in combination with a fixed dosage of isotretinoin (cRA) as shown in the table below. A cycle of treatment was 28 days (+ 3 days); the treatment schedule began with cRA on days 1-21. The total daily dose was to be given orally, divided BID (twice a day). Vorinostat was administered on days 1-14. The total daily dose was given once daily orally. Days 22-28 was considered as a no-treatment "rest" period.

A conventional phase I design was used with 3 patients enrolled into the first dose level and monitored for 3 weeks. If no DLT was seen, the next 3 patients were to be enrolled at the next dosage level. A maximum of three dosage levels will be utilized as shown in the table below. If no DLT was noted after dose escalation to Level III,

these doses were to be utilized for the phase II components of the study. If 1/3 patients shows \geq grade 3 toxicity, the cohort was to be expanded to 3 more patients, If 2/6 patients experience \geq grade 3 toxicity, the DLT was considered reached, and previous (lower) dosage level was to be declared as the MTD of vorinostat in combination with cRA.

Level	Arm 1		
	Vorinostat (mg/day x 14 days)	cRA (mg/m2/day x 21 days)	
0 (starting dose)	300 mg	100	
1	400 mg	100	
II	500 mg	100	

This arm of the trial completed accrual as planned and an MTD was established for the combination of vorinostat (400 mg/day on days 1-14) and isotretinoin (100 mg/m2/day on days 1-21) on a 28 day schedule. We propose to use this dose in the phase II trial.

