5.3. Definition of dose limiting toxicities (DLT)

Toxicities will be graded according to the Common Terminology Criteria for Adverse events (CTCAE) Version 3.0. (see Appendix B). If multiple toxicities are seen, the presence of DLT should be based on the most severe toxicity experienced. DLT will be defined as any of the following events occurring during treatment and attributable to the study drugs:

5.3.1 Any grade 4 hematological toxicity excluding lymphopenia . (if the toxicity is Grade 4 neutropenia without fever, it must NOT resolve/regress to \leq Grade 1 within 7 days of onset to be considered a DLT).

5.3.2 Any non-hematologic grade 3 toxicity, weight gain (in patients on steroids), alopecia, and venous thromboembolic disease *. Grade 3 nausea, vomiting, or diarrhea that cannot be controlled by medical therapy will be considered dose-limiting. Isolated laboratory abnormalities not of clinical significance will be discussed with the IRB and the decision to declare these DLTs will be based on the IRB recommendations.

5.3.3 Failure to recover from toxicities to be eligible for re-treatment within 4 weeks of the last dose of the drugs.

*Non-Relevant Toxicities for Brain Tumor Protocols

Lymphopenia is a common finding among patients with primary brain tumors and is directly attributable to concurrent use of corticosteroids. To date, even Grade III lymphopenia has not been associated with a worsening of clinical outcome. Therefore, we will not consider this parameter in the determination of optimal dosing of drugs.

Weight gain is a common finding among patients with primary brain tumors. This too is directly attributed to the concurrent use of corticosteroids. Doses of steroids or study agents will not be modified as a consequence of weight gain. Corticosteroid dosage will be based on maintenance of control of edema in the brain and the standard clinical practice to use the minimal effective dose of corticosteroids will be employed.

Alopecia is a common occurrence in patients with brain tumors as a consequence of cranial radiotherapy. Alopecia will not be recorded or graded as toxicity.

Venous thromboembolic disease is a common complication occurring in up to 30% of patients with malignant gliomas [32, 33]. In this study, patients who develop deep vein thrombosis may receive anticoagulation and resume therapy once they are stable on anticoagulation. Grade III deep vein thrombosis will not be considered a DLT.

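### Arm 3 dose decisions can be taken after 3 weeks, but amylase, lipase and lipids have no scheduled on-treatment result until about day 56, and no DLT window is stated

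*Combined protocol and SAP*

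**What the plan says.** Section 7.1 sets two chemistry schedules. For the general panel (electrolytes, renal and liver tests, coagulation) it says "all patients will have the following tests every 2 weeks (± 3 days) for the first cycle". The pancreatic enzymes and lipids are separated from that panel: "All patients will have serum amylase, lipase, and lipid panel drawn every 2 cycles of treatment". The next sentence adds that "Patients may also be evaluated with labs at any time clinically indicated". Section 6.3 places the baseline for all of these tests before treatment.

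Section 5.3.2 makes "Any non-hematologic grade 3 toxicity" a DLT, with listed exceptions. It sends isolated laboratory abnormalities without clinical significance to the IRB for a decision. Section 5.3 sets no time limit beyond the event occurring while on treatment, and 5.3.3 adds failure to recover within 4 weeks of the last dose.

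Section 3.1.7 includes "elevated triglycerides, pancreatitis" among the serious side effects of isotretinoin. Section 4.10 requires normal amylase and lipase before therapy but accepts raised cholesterol and triglycerides.

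The one cohort observation period in the protocol is in 5.1.1, for Arm 1, where patients are "monitored for 3 weeks". Sections 5.1.3 and 11.1.3 carry the Arm 1 enrolment scheme to Arm 3 by reference and give no separate period.

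**The concern.** The MTD rule in 5.1.3 counts DLTs in cohorts of 3 or 6 patients. A count of this kind is only as good as the observation behind it, because an event for which no test was done is scored as no event. For three tests that the protocol itself links to serious isotretinoin toxicity or to eligibility, the first scheduled on-treatment value comes well after the cohort may be closed. The rest of the chemistry is drawn in time.

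At stake is the dose of a three-drug combination that goes straight into Phase II. Symptom-free abnormalities that 5.3.2 could count, or that the IRB might have been asked to rule on, would normally be unknown when the next cohort opens. Because 5.3 has no window, the protocol also does not say whether a cycle-2 result that arrives before the MTD is declared should change the count.

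**Working it through.** The plan states no figure for this point, so the check is a comparison of dates followed by an illustration.

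**Inputs.** Cycle of 28 days, with up to 3 days' leeway (5.1.1). Amylase, lipase and lipids every 2 cycles (7.1). Cohort observation of 21 days (5.1.1, by reference in 5.1.3). MTD exceeded at 2 or more of 6 (5.1.3.2). Phase II accrual of 3 to 5 patients per month and a historical median PFS of 3 months (11.2). Phase I accrual is not given, so the Phase II rates are borrowed as an assumption: one patient about every 10 or 6 days.

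**1. First scheduled draw.** 2 × 28 = day 56, or 2 × 31 = day 62 at most. This is 56 − 21 = 35 days after the observation period and 56 − 28 = 28 days after the end of cycle 1. The words of 7.1 do not literally fix the first draw; after cycle 2 is the natural reading, given the pre-treatment baseline. The 2-weekly panel, by contrast, has a draw at day 14 ± 3, that is day 11 to 17, inside the 21 days.

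**2. Three-patient decision.** The decision falls 21 days after the third patient starts. With spacing s between patients, the first patient is then at day 2s + 21.
- s = 10: day 41.
- s = 6: day 33.

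Nobody has reached day 56. The first patient would do so only if s were at least (56 − 21)/2 = 17.5 days.

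**3. Six-patient decision** (three patients, 21 days' observation, three more patients, 21 days' observation).

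| Spacing | Patients 1–3, day at decision | Patients 4–6, day at decision |
|---|---|---|
| 10 days | 82, 72, 62 | 41, 31, 21 |
| 6 days | 66, 60, 54 | 33, 27, 21 |

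Two or three of the first three patients, if still on treatment, would have passed day 56. None of the last three would.

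**4. Illustration only.** Let p be the rate of other DLTs and q the rate of laboratory-only events that would count as DLTs, taken as independent, so that the total is t = 1 − (1 − p)(1 − q). Both rates are assumptions. With p = 0.20:

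| q | t | No DLT in 3: (1 − t)³ | 0–1 DLT in 6: (1 − t)⁶ + 6t(1 − t)⁵ |
|---|---|---|---|
| not measured | 0.20 | 0.512 | 0.655 |
| 0.05 | 0.24 | 0.439 | 0.558 |
| 0.10 | 0.28 | 0.373 | 0.464 |
| 0.20 | 0.36 | 0.262 | 0.301 |

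With p = 0.10, the 6-patient figure is 0.886 unmeasured, against 0.788, 0.680 and 0.464. With p = 0.30, it is 0.420 against 0.348, 0.283 and 0.176. The 6-patient contrasts are upper limits: step 3 shows that some early patients may have a result, and 5.3.2 does not make every abnormality a DLT.

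**5. First Phase II safety look** (after 10 patients per arm, 9.1 and 11.2). Thirty patients take 30/3 = 10 or 30/5 = 6 months. Fifty-six days is 56/30.4 = 1.84 months, in which 3 × 1.84 = 5.5 or 5 × 1.84 = 9.2 patients enrol. About 24 or 21 of the 30 are therefore past day 56. If PFS is exponential with the 3-month median, 0.5^(1.84/3) = 0.65 are progression-free at day 56, which leaves about 16 or 14 with a scheduled draw.

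**The case against.** A reader might infer that these toxicities cannot enter the Arm 3 MTD decision at all. The documents do not support that. Symptomatic pancreatitis of grade 3 or more is a clinical DLT under 5.3.2 without any scheduled draw. Section 7.1 allows laboratory tests whenever clinically indicated. Section 5.3 counts events throughout treatment, so a day-56 value from an early patient could count if the MTD has not yet been declared.

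A reader might also infer that the first Phase II safety look has no on-treatment values for these tests. It comes 6 to 10 months into accrual, when most enrolled patients are past day 56.

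Three further objections carry weight:
- Abnormalities without clinical significance go to the IRB and are not automatic DLTs. Raised triglycerides at baseline are accepted.
- Isotretinoin is fixed at one dose across all Arm 3 levels, so an effect due to isotretinoin alone would not separate them.
- No event rate is given, and the table in 3.2.7 of vorinostat-related events in at least 10% of 305 patients lists no amylase, lipase or lipid event.

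These narrow the point but do not remove it. A clinically indicated test needs a clinical prompt, which a symptom-free rise does not supply. The IRB cannot rule on a value that was never drawn. A fixed isotretinoin dose does not keep its events out of the 2-of-6 count. The missing window leaves undecided how a late result should be used.

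**Conclusion.** The point holds as a mismatch between the laboratory schedule and the cohort decision. It is limited to symptom-free grade 3 or higher rises in triglycerides, amylase or lipase. Liver tests and blood counts are drawn during cycle 1 and are not affected.

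At a 3-patient decision no patient has a scheduled result, provided patients enter less than 17.5 days apart. At a 6-patient decision the later three have none under the assumed accrual. The gap is 35 days from the end of the stated observation period. This rests on reading the first draw as falling after cycle 2 and on the 3 weeks of Arm 1 applying to Arm 3.

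The probabilities in the working show the direction and possible scale. They are not estimates, because the documents give no rate and not every abnormality would be a DLT. The change is worth making because it is cheap and the dose carries into Phase II; the finding does not show that any chosen dose would be wrong.

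**What to change.** Reconcile 5.1.1, 5.3 and 7.1 for Arm 3. State the DLT observation period explicitly, and say whether a result that arrives after it but before the MTD is declared counts. Then make sure that each laboratory test able to define a DLT has at least one scheduled on-treatment result within that period. One way is to add amylase, lipase and the lipid panel to blood draws that 7.1 already schedules in cycle 1. The timing is for the sponsor to choose.

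The cost is three extra assays per patient on samples already taken, and a few lines of text; no visit is added. A draw at about day 14 fits the existing 3 weeks but leaves the third week of isotretinoin unobserved. A draw before cycle 2 covers the whole dosing period but, if the decision waits for it, adds up to about 28 − 21 = 7 days per cohort. More results may also mean more referrals to the IRB.

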5.4. Dose modifications

5.4.1 Subsequent Cycles

Treatment cycles will be repeated every 28 days (+ 2 days) from day 1 provided that the tumor has not progressed and the patient has recovered from treatment-related adverse events associated with a prior course. Recovery has occurred once all of the following conditions have been met:

a) ANC >1500/mL;

b) Platelet Count >100,000/mL;

c) All drug-associated non-hematological toxicities have recovered to either Grade 0 or 1(except for deep venous thrombosis as below).

If recovery has not occurred by **Day 28** (+ 3 days), the subsequent cycle will be delayed until these criteria have been met. If the patient has not recovered within 4 weeks of rest, he/she will be taken off study. However, if the patient develops a lower extremity deep venous thrombosis and requires anticoagulation or intervention (grade 3 toxicity), treatment may be restarted after a 2 week rest period if the patient

is stably anticoagulated and is judged medically stable to begin chemotherapy, in the opinion of the treating physician. (Please note: DVT is graded in the CTC version 3.0 as grade 1= not defined, grade 2= DVT without need for anticoagulation or intervention, grade 3= DVT needing anticoagulation or intervention).

The administration of vorinostat, isotretinoin and temozolomide in subsequent cycles will continue at the same doses without interruption as long as there is no tumor recurrence or progression and toxicity is acceptable.

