5.4.2 Dosage Reduction

Patients experiencing toxicity will be dose reduced according to the agent causing the toxicity. Because of the different profile of side effects of agents combined in Arms 1 and 2 (vorinostat + cRA; TMZ + cRA), no significant overlapping toxicities are expected. In case of thrombocytopenia or anemia in Arm 3 (vorinostat + cRA + TMZ), temozolomide will be dose-reduced first, and then vorinostat on an alternating basis for each time a dose reduction becomes necessary.

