5.4.2.1 Vorinostat

Vorinostat will be administered from day 1 -14 in arm 1 and on days 1-7 and 15-21 in arm 3. Treatment will be initiated at the MTD dose determined in the phase I component of the trial for each arm. This dose will be maintained as long as there are no toxicities \geq grade 3. For grade 3 or greater toxicities, treatment will be withheld and the patients will be monitored until toxicities resolve to < grade 2 (except for deep venous thrombosis as noted in section 5.3). Subsequent treatment will be at one dose level lower than the one that caused the toxicity. If there is grade 3 or greater non-hematologic toxicity, a minimum of 2-week rest period will be required. Subsequently, patients will restart treatment at one dose level less than the one that resulted in the toxicity as indicated below.

Dose adjustments for the subsequent cycles: dose will be one level below the dose that produced toxicity of grade 3 or greater per dose schedule changes indicated below. If grade 3 or 4 toxicity recurs, patients will again discontinue the vorinostat until toxicity returns to grade 1 or less. The estimated dose levels below are shown for various MTD that may be determined in the phase I study.

In case of thrombocytopenia or anemia in Arm 3 (vorinostat + cRA + TMZ), TMZ will be dose-reduced first, and then vorinostat on an alternating basis for each time a dose reduction becomes necessary.

Dose Level:	-2	-1	0
Drug			MTD Phase I
Vorinostat	N/A	200 mg once daily	300 mg once daily
	200 mg once daily	300 mg once daily	400 mg once daily

300 mg once daily	400 mg once daily	500 mg once daily

Only 2 dose reductions of vorinostat are permitted as above. If the patient experiences grade 3 or greater toxicity after 2 dose reductions, he/she will be taken off study. If starting dose is 300 mg once daily, only 1 dose reduction of vorinostat is allowed.

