- **8.2.5 Progression:** 25% increase in the sum of products of all measurable lesions over smallest sum observed (over baseline if no decrease) using the same techniques as baseline, OR clear worsening of any evaluable disease, OR appearance of any new lesion/site, OR failure to return for evaluation due to death or deteriorating condition (unless clearly unrelated to this cancer).
- **8.2.6** Unknown: Progression has not been documented and one or more measurable or evaluable sites have not been assessed.

8.3 Note:

- **8.3.1** For evaluable disease other than types specified in Section 8.1.2, the only objective statuses which apply are CR, stable/no response, progression and unknown.
- **8.3.2** Objective status must stay the same or improve over time until progression (unknown excepted).
- 8.4 Neurological Exam: Although not used for determining response, it is useful to evaluate improvement in the neurologic exam that should coincide with objective measurement of tumor size.

- 1 Normal exam
- 2 Improvement from on-study state (patient better)
- 3 Same as on-study state (patient same).
- **4** Worse than on-study state (patient worse).
- **8.5** **Performance Status:** Patients will be graded according to Karnofsky Performance Status (see Appendix G).
- 8.6 **Progression Free Survival (PFS)**: From date of registration to the date of first observation of progressive disease, non-reversible neurologic progression or permanently increased steroid requirement (applies to stable disease only) or death due to any cause. Progression Free Survival (PFS) in patients enrolled in the surgical arm will be determined from the date of randomization (i.e. after surgery for resection of recurrent tumor), and not from the date of registration in the trial.
- 8.7 **Survival:** From date of registration to date of death due to any cause.
- **8.8** Steroids: Steroid dosage will be carefully monitored and recorded during each course of therapy and steroid dosage changes will be considered before response determinations are made.
- **8.9** Unacceptable toxicity: grade 3 or greater toxicity after 3 dose reductions of temozolomide or 2 dose reduction of any of the other drugs, or after 1 dose reduction if starting dose of vorinostat is 300 mg orally once daily.

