12.0 COMPLIANCE AND DATA MANAGEMENT

12.1 Protocol Compliance:

The attending physician and oncology research nurse must see each patient after the first cycle, and subsequently after each 2 cycles of treatment prior to initiating the next cycle. All required interim and pretreatment data should be available and the physician must have made a designation as to tumor response and toxicity grade.

12.2 Data Entry:

All data will be entered on the computerized Protocol Data Management System (PDMS) of the Division of Medicine at MDACC. Patients must be registered in PDMS before a course of therapy can be given. A brief explanation for required but missing data should be recorded as a comment.

12.3 Accuracy of Data Collection:

A group consisting of the study chairman, the department chairman, the deputy chairman and an faculty member from the neuroradiology department will be the final arbiter of response or toxicity should a difference of opinion exist. The study chair will have the deciding vote in case of a tie.

Any life-threatening and/or unexpected and serious (grade 3 or 4) toxicity will be reported within 5 working days to the Study Chairman who, in turn, must notify the Surveillance Committee and the sponsoring agencies (See Appendix A).

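### Scheduled MRI follows the cycle count, so unequal toxicity delays would date PFS later in the more delayed arm; a calendar scan schedule is a cheap improvement

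*Combined protocol and SAP*

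**What the plan says.** **Scan clock.** Section 7.3: "A Gd-DPTA MRI scan shall be done after each" two cycles, before the next cycle. I found no calendar anchor. Examinations (7.4) and physician visits (12.1) also follow the cycle count. Both are required after cycle 1, and 12.1 then continues "subsequently after each 2 cycles of treatment prior to initiating the next cycle"; 7.4 also requires an examination after cycle 2.

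**Slippage.** Cycles are nominally 28 days. If recovery is incomplete, "the subsequent cycle will be delayed until these criteria have been met" (5.4.1). The limit is in the same section: "If the patient has not recovered within 4 weeks of rest, he/she will be taken off study".

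**Event date.** PFS runs "to the date of first observation of progressive disease", or to non-reversible neurologic progression, a permanently increased steroid requirement, or death (8.6).

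**Use of PFS.** Under 11.2, observed failure times drive the adaptive randomization, the dropping of arms, early stopping and final selection.

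**Rules that could make delays unequal.** For vorinostat, after grade 3 or greater non-hematologic toxicity, "a minimum of 2-week rest period will be required" (5.4.2.1); isotretinoin has the same rest (5.4.2.2). Temozolomide is postponed week by week, for at most 4 weeks (5.4.2.3). For Arms 1 and 2, 5.4.2 says that "no significant overlapping toxicities are expected". For Arm 3 it adds a rule: "In case of thrombocytopenia or anemia in Arm 3 (vorinostat + cRA + TMZ), temozolomide will be dose-reduced first".

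**Features that limit the effect.** MRI (7.3) and evaluation (7.4) are allowed whenever clinically needed. Failure to return because of deterioration counts as progression (8.2.5). Doses are reduced for toxicity (5.4.2). Failure to recover within 4 weeks of the last dose is a DLT (5.3.3), and an arm that reaches the DLT limit is modified or closed (9.1).

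**The concern.** A progression first seen on a scheduled scan takes the date of that scan. If one arm's cycles slip more, its scans slip with them and its observed PFS lengthens with no difference in disease. In a fixed-allocation trial this would affect only the final comparison. Here the observed times also steer allocation as patients enter, so the artefact feeds back during accrual. Two things are at stake: an arm no better than the others could be favored because it is delayed more, and a truly better arm with fewer delays could be selected less often. Scans not done on time cannot be recovered at analysis.

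**Working it through.** **Inputs from the documents.** Cycle 28 days; delay of at most 4 weeks per cycle (5.4.1). From 11.2: null median 3 months; first 30 patients randomized equally; maximum 135; 6 months of further follow-up; 3 or 5 patients per month; prior (2.009, 3.027) per arm; minimum randomization probability 0.1; cut-offs 0.975 (early selection), 0.85 (final selection), and 0.01 for suspending an arm, both against the best arm and against 3 months.

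**Assumptions.** Exponential PFS. The prior is read as inverse gamma on the median, with mean 3.027/(2.009 − 1) = 3.0. Share of cycles delayed by arm, each delay lasting 1, 2, 3 or 4 weeks. Share of progressions found clinically at onset rather than by scheduled scan. Event-free patients counted either to the last scan or to the analysis date, because the supplied text does not state the censoring date.

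**Step 1: reproduce the plan.** The posterior of an arm's median is IG(2.009 + events, 3.027 + ln2 × exposure). With events dated exactly, at 3 per month:

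| True medians | Simulated Pr(selected) | Stated |
|---|---|---|
| 3/3/3 | 0.056/0.048/0.057 | 0.054/0.051/0.061 |
| 3/4/5, Arm 3 | 0.537 | 0.54 |
| 3/3/7, Arm 3 | 0.996 | 0.995 |

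A second coding of the same rules agreed on Scenarios 1, 4 and 5 but ran high on Scenarios 2 and 3 (0.569 against 0.54 and 0.787 against 0.758 at 3 per month; up to 0.555 against 0.492 at 5 per month). Differences of a point or two below should not be over-read.

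**Step 2: dating effect in one arm.** If every progression is found at a scan with interval d months, mean observed PFS is d/(1 − exp(−d·ln2/3)), and the fitted median is ln2 times that.

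| Interval | Fitted median (true 3) | Against 56 days |
|---|---|---|
| 56 days | 3.68 | 1.00 |
| 70 days | 3.87 | 1.05 |
| 84 days | 4.06 | 1.10 |
| 112 days (both cycles delayed 4 weeks) | 4.45 | 1.21 |

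**Step 3: from delay rate to interval.** With a share p of cycles delayed and a mean delay of 2.5 weeks, the mean interval is 8 + 2 × p × 2.5 weeks: 8.5 weeks at p = 0.1, 9.5 at 0.3 and 10.5 at 0.5.

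**Step 4: equal true medians of 3 months.** Arm 3 serves only as the example of a delayed arm.

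| Cycles delayed; detection; accrual | Delayed arm selected | Each other arm | Patients |
|---|---|---|---|
| 10/10/50%; all by scan; 3/month | 0.034–0.062 | 0.011–0.020 | 49–51 v 40–43 |
| 10/10/50%; 70% by scan; 3/month | 0.058–0.065 | 0.021–0.025 | 48–50 v 41–42 |
| 10/10/50%; half clinical; 3/month | 0.038–0.071 | 0.022–0.036 | 46–48 v 42–45 |
| 10/10/50%; all by scan; 5/month, to analysis date | 0.075–0.078 | 0.015–0.029 | 50 v 40 |
| 30% v 10%; all by scan; 3/month | 0.026–0.037 | 0.015–0.020 | – |
| 30% v 10%; half clinical; 3/month | 0.034 | 0.024–0.036 | – |
| Calendar 8 weeks; 3/month | 0.017–0.041 in every arm, no tilt | | 43–45 each |

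Runs used 1,500 to 4,000 trials (standard error about 0.002 to 0.004 in the larger ones).

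**Step 5: an undelayed arm is truly better (Arm 2, 3/month).** Probability of selecting it:

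| Medians; detection | Calendar | 10% in all arms | 10/10/50% |
|---|---|---|---|
| 3/4/3; all by scan, to last scan | 0.328 | 0.322 | 0.25–0.27 |
| 3/4/3; all by scan, to analysis date | 0.352 | 0.352 | 0.288 |
| 3/4/3; half clinical | 0.371 | 0.376 | 0.32–0.34 |
| 3/5/3; all by scan | 0.783 | 0.776 | 0.72–0.73 |
| 3/5/3; half clinical | 0.808 | – | 0.79 |

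Standard error at 3/4/3 is 0.008 to 0.009.

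**The case against.** The strongest reply is that the 50% case runs into the protocol's own brakes. The last Arm 3 dose is on day 21, so a 4-week wait after day 28 ends 5 weeks after the last dose and is a DLT under 5.3.3 if attributed to study drug. With equal weights for the four delay lengths, 0.5 × 0.25 = 12.5% of cycles would produce one. That is 1 − 0.875² = 23% of patients after two cycles and 1 − 0.875³ = 33% after three, which is where 9.1 acts. The simulations model neither this nor dose reductions, nor any efficacy lost through delay, which would oppose the tilt. This stands as a reason to expect a smaller effect. It does not remove it: waits of 1 to 3 weeks do not meet 5.3.3, and 50% against 10% with those waits alone (mean 2 weeks) still gives intervals of 8 + 2 × 0.5 × 2 = 10.0 against 8 + 2 × 0.1 × 2 = 8.4 weeks.

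It is also fair that clinical detection shrinks the tilt. In one half-clinical setting at 10/10/50% the arms were selected 0.026/0.032/0.038, which is hardly distinguishable. The examination and visit after cycle 1 help, since early cycles matter most with a 3-month median.

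A reader might infer that the three-drug arm will be favored. The documents do not support that. The Arm 3 rule in 5.4.2, and the poor tolerance of the earlier carboplatin-containing three-drug regimen (2.11), make unequal delays plausible but give no rate and no ranking for the present arms.

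**Conclusion.** The point holds as a cheap improvement. Cycle-linked scans, delays of up to 4 weeks and dating at first observation are all in the text. Together they let unequal delays tilt a PFS-driven design modestly toward the more delayed arm. Under 10/10/50% delays that arm is selected with probability about 0.03 to 0.08, against about 0.01 to 0.04 for each other arm. A better undelayed arm loses about 0.06 to 0.08 of its selection probability at medians 3/4/3 if all progressions are scan-found, and about 0.03 to 0.06 if half are clinical. These sizes rest on assumed delay rates and detection shares, and the brakes above are not modelled.

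Two stronger readings should be avoided. One is that the stated error rates are wrong: they reproduce under exact event dating, and the delayed arm usually stays near or below the stated per-arm maximum (0.061 at 3 per month, 0.055 at 5 per month). The other is that those figures cap the effect: with patients counted to the analysis date the delayed arm can reach about 0.07 to 0.08.

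Survival-only follow-up after treatment (7.8) is not a further bias finding. Stopping without progression, with censoring at the last disease assessment, added no inflation in simulation.

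**What to change.** Amend 7.3 to the effect of: *PFS-assessment MRI every 8 weeks (± 1 week) from the PFS start date in 8.6 (registration; randomization for surgical patients), regardless of cycle delays, while on treatment; additional MRI when clinically indicated.*

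Reconcile this with the present requirement in 7.3 for a scan before the next cycle, and with the 5.4.1 condition that the tumor has not progressed, so that it is clear which scan serves which purpose. No treatment rule needs to change.

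Cost: a wording amendment. Undelayed patients keep the same 8-week frequency. Under the 50% assumption, delayed patients have about 52.2/8 = 6.5 scans per year on treatment instead of 52.2/10.5 = 5.0, and more if a separate pre-cycle scan is kept. Some scans will fall between cycles.

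Optional clarification: state in 11.2 the date at which event-free patients are censored, and in 7.8 whether progression found after stopping treatment is recorded. Appendix H, which was not available, may already settle the censoring date.
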